## 18.0 Confidentiality

### A. Confidentiality of Study Data

*Describe the local procedures for maintenance of confidentiality of **study data and any records that will be reviewed for data collection.***

*18.1 A. Where and how will all data and records be stored? Include information about: password protection, encryption, physical controls, authorization of access, and separation of identifiers and data, as applicable. Include physical (e.g. paper) **and** electronic files.*

Response: All patients' data records will be stored on password protected computers and or in locked cabinets within the research department. The research unit is locked after 5pm daily and all day on weekends. Identifiable patient information along with randomization information for each patient will be stored in locked cabinets in a locked archive room. This will only be accessible by study coordinator and the PI. Electronic data will be stored on password protected computers as coded data based on randomization number eg R-12 without any patients identifiable information attached. These electronic files will only be accessible by authorized study personnel.

*18.2 A. How long will the data be stored?*

Response: Data and specimens storage has no expiration date and will be stored for a minimum of 7 years. The researchers may continue to rely on this for future use in research study. Identifiable patient information will be destroyed after 3 years of study completion.

*18.3 A. Who will have access to the data?*

Response: Those physicians, nurses, and laboratory staff that are on all documentation for the study will have access to the data and specimens

*18.4 A. Who is responsible for receipt or transmission of the data?*

Response: Those physicians, nurses, and laboratory staff that are on all documentation for the study will have access to the data and specimens and can handle transfer of data and samples

*18.5 A. How will the data be transported?*

Response: All data are stored at one location and is not transported unless it is being archived. At that point files will be transferred to Iron Mountain for storage and archiving.

## **B. Confidentiality of Study Specimens**

*Describe the local procedures for maintenance of confidentiality of study specimens.*

- N/A:** No specimens will be collected or analyzed in this research.  
(Skip to Section 19.0)

*18.6 B. Where and how will all specimens be stored? Include information about: physical controls, authorization of access, and labeling of specimens, as applicable.*

Response: The specimens will be stored in the CRC laboratory located at [name] and at the CTRC located in [name]. Samples will be stored in a locked -80° C freezers. Ultimately, all specimens will be transported to CTRC location for banking. Specimens will be labeled as a coded sample, using the patient's randomization number (e.g. R-12), visit time and number and sample type. Specimens will not be stored with any patient identifiable information which is kept in locked cabinets in the CRC at [name].

*18.7 B. How long will the specimens be stored?*

Response: Data and specimens storage has no expiration date and will be stored for a minimum of 7 years. The researchers may continue to rely on this for future use in research study

*18.8 B. Who will have access to the specimens?*

Response: Those physicians, nurses, and laboratory staff that are on all documentation for the study will have access to the data and specimens

*18.9 B. Who is responsible for receipt or transmission of the specimens?*

Response: : Those physicians, nurses, and laboratory staff that are on all documentation for the study will have access to the data and specimens and can handle transfer of data and samples

*18.10 B. How will the specimens be transported?*

Response: All data are stored at one location and is not transported unless it is being archived. At that point files will be transferred to Iron Mountain for storage

and archiving. Samples that are transported will be done so using dry ice in a properly labeled Styrofoam container by the laboratory technician

## 19.0 Provisions to Monitor the Data to Ensure the Safety of Subjects

- N/A:** This study is not enrolling subjects, or is limited to records review procedures only. This section does not apply.

***NOTE: Minimal risk studies may be required to monitor subject safety if the research procedures include procedures that present unique risks to subjects that require monitoring. Some examples include: exercising to exertion, or instruments that elicit suicidality or substance abuse behavior. In such cases, N/A is not an acceptable response.***

*19.1 Describe the plan to periodically evaluate the data collected regarding both harms and benefits to determine whether subjects remain safe.*

Response: [name], an independent clinician has been designated to provide review of accumulating safety data. Along with the principal investigator [name], PhD and co-investigators [name] and [name] they will review the data every 3 months to assess the safety and potential benefits to the participant. Furthermore, they will also assess other risks including the physical, psychological, social, legal and economic harm to these patients. The investigators listed above will carefully watch for any invasion of privacy and breach of confidentiality. The principal investigator will be sharing the results of safety analysis of the study with the sponsor (AZ) and to the IRB. The study groups will remain blinded. If there are any safety concerns, [name] (PhD), who is not directly involved in patients care or insulin titrations, is designated to unblind the study groups based on the discretion of the principal investigator and the recommendation by the independent monitor. [name] role will be to tabulate and present unblinded data to the investigators and [name] for review. Based on review of the data presented, assessment of potential harm to the patients will be carried out to determine the best course of action. The IRB and sponsor will be informed of this potential harm along with the recommended course of action. Research subjects will be withdrawn from the study if risks outweigh the benefits (see subject withdrawal section). The IRB will be kept well-informed at all times

*19.2 Describe what data are reviewed, including safety data, untoward events, and efficacy data.*

*Response:* Patients CGM, dietary intake, BP, weight are monitored every visit to ensure safety. CGM graphs will be evaluated every visit to reduce risk of hypoglycemia or hyperglycemia. STAT CMP will be done when glucose or

ketones exceeds 400mg/dl and 2.5mM, respectively or any signs of DKA is observed during the acute testing phase and will be reviewed the same day. Safety assessments will consist of monitoring and recording all TEAEs, SAEs, AEs leading to discontinuation/withdrawal from study, laboratory evaluation for hematology, blood chemistry, and urine values; pregnancy testing; measurement of vital signs; and performance of physical examinations.

*19.3 Describe any safety endpoints.*

Response: Safety data (vitals, CBC, CMP, urinary markers) will be collected at screening, during and at end of the study. *STAT CMP will be done when glucose or ketones exceeds 400mg/dl and 2.5mM, respectively or any signs of DKA is observed during the acute testing phase.*

*19.4 Describe how the safety information will be collected (e.g., with case report forms, at study visits, by telephone calls with participants).*

Response: The safety information will be collected at the time of the participants visit, and or during telephone calls with the participant.

*19.5 Describe the frequency of safety data collection.*

Response: The data collection will be done at all study visits which will be at intervals of either one or two weeks depending on the number of study visit. The patients, however, will be asked to report any adverse event or safety related information via phone as soon as it occurs and it will be reviewed the same day.

*19.6 Describe who will review the safety data.*

Response: The independent clinician monitor along with the principal investigator [name], PhD and co-investigators, [name], MD, [name], MD* and [name] will review the data at the completion of all visits by each subject and every 3 months to assess the safety and any potential risks to the participants. Furthermore they will also assess other risks including the physical, psychological, social, legal and economic harm to these patients. The investigators listed above will carefully watch for any invasion of privacy and breach of confidentiality. The principal investigator will be sharing the results of safety analysis of the study with the sponsor (AZ) and with the IRB. The study groups will remain blinded. If there are any safety concerns then co-investigator [name] who is not directly involved with the study participants will unblind the study groups on the discretion of principal investigator and present the analyzed data to the clinician monitor and investigators.

*19.7 Describe the frequency or periodicity of review of cumulative safety data.*

*Response: Safety data will be reviewed every 3 months. Study endpoint data will be reviewed once after half of the recruited patients have completed the study and then at the end of the study.*

*19.8 Describe the statistical tests for analyzing the safety data to determine whether harm is occurring.*

Response: The statistical analysis will be carried out using the student t-test or Wilcoxon's test for paired data

*19.9 Describe any conditions that trigger an immediate suspension of the research.*

Response:

1. Any episode of DKA occurring in >15% (placebo-adjusted) of participants.
2. Pancreatitis occurring in > 5 % (placebo-adjusted) of participants
3. New information becoming available concerning the safety of study drugs
4. Termination of funding.

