## 4.0 Study Design

### 4.1 Describe and explain the study design (e.g. case-control, cross-sectional, ethnographic, experimental, interventional, longitudinal, observational).

*Response:* The first 60 patients (cohort 1) will be involved in a single center, prospective, double blind, randomized, placebo –controlled in a parallel design study. The last 20 patients (cohort 2) will be enrolled into a single centered, prospective, randomized, open labeled study. The study will be conducted at the Diabetes – Endocrinology Center of Western New York under the direction of [name], M.D, [name], MD, [name] and [name], PhD.

In the first cohort, sixty (60) patients with T1D will be enrolled and randomized into 4 groups (15 each) to receive placebo, or dapagliflozin, or exenatide (5µg acutely)/Exenatide extended release (2mg weekly subcutaneous injection, long term), or exenatide (5µg acutely)/Exenatide extended release (2mg weekly subcutaneous injection, long term) and dapagliflozin treatments acutely and for 12 weeks.

The treatment arms of this study are:

1. Placebo Arm: dapagliflozin placebo (oral tablet) and exenatide (5µg acutely)/Exenatide extended release (long term) placebo (subcutaneous injection)
2. Dapagliflozin Arm: dapagliflozin 10mg (oral tablet) and exenatide (5µg acutely)/Exenatide extended release (long term) placebo (subcutaneous injection)
3. Exenatide/Exenatide extended release Arm: subcutaneous injection of Exenatide (5µg acutely)/Exenatide extended release 2 mg weekly injection (long term) and dapagliflozin placebo
4. Exenatide/Exenatide extended release & dapagliflozin Arm: Exenatide (5µg acutely)/Exenatide extended release 2 mg weekly injection (long term) and dapagliflozin 10mg

In the second cohort, twenty (20) patients will be randomized into three groups.

1. Open-label Dapagliflozin
2. Open-label Bydureon/Byetta
3. Open label Bydureon/Byetta and open label Dapagliflozin

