All drugs used and their matching placebos will be provided by AstraZeneca in an unlabeled form. Drug or placebo assignment will be mailed separately. A designated coordinator/investigator (or University Pharmacy) who is not participating in the study will receive the drug/placebo assignment codes and will be responsible for relabeling the drugs and placebo containers/vials according to Good Manufacturing Practice and in compliance with FDA regulations and local guidelines. Relabeled drug/ placebos will be dispensed by study investigators according to pre-generated randomization log generated using Microsoft –Excel randomization feature. Records of drug and placebo assignment will be kept with the independent investigator/coordinator (or UB Pharmacy) in a secure place (locked office or enclosure) or on password protected computer and folder (if digital) For each patients and in at every dispensing visit, 2 drugs and/or placebos combo will be dispensed to maintain blinding of both patient and study team. For example, patients in the dapagliflozin only arm will receive dapagliflozin active drug tablet and exenatide (acute study) and exenatide extended release (long term) matching placebos.

Drugs will be stored in a locked cabinet or locked temperature controlled refrigerator at 4C at the research facility of the Diabetes and Endocrinology Center of WNY. IND application for use of all drugs (dapagliflozin, Exenatide extended release and exenatide) in type 1 diabetes will be submitted to FDA and no study procedure will start before all local and federal approvals are obtained.

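### The placebo-adjusted suspension triggers cannot be evaluated at the blinded safety reviews, and their denominator and cohort 2 comparator are undefined

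*Combined protocol and SAP*

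**What the plan says.** Section 19.9 lists four conditions for immediate suspension. Two are event rates: "Any episode of DKA occurring in >15% (placebo-adjusted) of participants" and "Pancreatitis occurring in > 5 % (placebo-adjusted) of participants". It does not say which patients form the denominator, how the adjustment is made or which arms are compared.

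Sections 19.1 and 19.6 both state that "The study groups will remain blinded". Both allow unblinding if a safety concern arises, but on different terms. In 19.1, a person with no direct role in patient care "is designated to unblind the study groups based on the discretion of the principal investigator and the recommendation by the independent monitor". In 19.6, a co-investigator not directly involved with participants "will unblind the study groups on the discretion of principal investigator and present the analyzed data to the clinician monitor and investigators". On timing, 19.7 says "Safety data will be reviewed every 3 months", and 19.6 adds a review when each subject has completed all visits. On the codes, section 10.1 says "Records of drug and placebo assignment will be kept with the independent investigator/coordinator", with the university pharmacy as the alternative.

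Under section 4.1, cohort 1 has 60 patients in four arms of 15, one of them placebo. Cohort 2 is the last 20 patients and is open label; there, "twenty (20) patients will be randomized into three groups", all of them active.

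**The concern.** A placebo-adjusted percentage is a difference between arms, and a blinded review shows only a total. Under 19.1 and 19.6, counts by arm follow a decision to unblind, and no number of events obliges anyone to take that decision. The trigger is meant to prompt action, yet it can be evaluated only after a discretionary action has been taken.

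DKA is the trial's main known hazard: section 3.1 reports two cases in 20 patients on triple therapy. Two things are at stake. The condition could be met in the arms at risk while a routine review cannot show it. And two careful readers holding the same unblinded table could disagree on whether it had been met.

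**Working it through.** **No plan figure to reproduce.** The 15% and 5% thresholds come with no event counts, derivation or operating characteristics. Section 19.8 names a t-test or a paired Wilcoxon test, neither of which is a rule for comparing event proportions between arms.

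**Inputs.** Thresholds from 19.9. Arm sizes from 4.1: 15 per arm in cohort 1, so 30 on dapagliflozin and 45 on any active treatment. Adding the 20 in cohort 2 gives 65 on active treatment.

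**Step 1: events needed under each reading.** The trigger is met at the smallest k with k/n − placebo rate > threshold, at full enrolment.

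| Denominator | DKA, 0/15 placebo | DKA, 1/15 placebo | Pancreatitis, 0/15 placebo |
|---|---|---|---|
| One cohort 1 arm, n = 15 | 3 (20.0%) | 4 | 1 (6.7%) |
| Cohort 1 dapagliflozin arms, n = 30 | 5 (16.7%) | 7 | 2 (6.7%) |
| Cohort 1 active arms, n = 45 | 7 (15.6%) | 10 | 3 (6.7%) |
| Active arms, both cohorts, n = 65 | 10 (15.4%) | 15 | 4 (6.2%) |

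**Step 2: what blinding hides.** Suppose 6 of 30 dapagliflozin patients in cohort 1 have DKA and nobody else does. The pooled rate is 6/60 = 10%. The adjusted rate is 6/30 − 0/15 = 20% over the dapagliflozin arms, which meets the trigger. Over all cohort 1 active arms it is 6/45 − 0/15 = 13.3%, which does not. The pooled count does not identify the adjusted rate: 4 cases among 60 (6.7%) could be one per arm (adjusted 0%) or all in one active arm (4/15 = 26.7%).

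**Step 3: how much the denominator matters.** The table gives the chance of exceeding 15% at full cohort 1 enrolment, in a single look. The true rates are assumptions, because the plan gives none; the exenatide-only and placebo arms share the rate called elsewhere.

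| True DKA rate on dapagliflozin / elsewhere | Any one active arm | 30 on dapagliflozin | 45 active |
|---|---|---|---|
| 10% / 0% | 33% | 18% | 3% |
| 20% / 0% | 84% | 74% | 39% |
| 30% / 0% | 98% | 97% | 84% |
| 10% / 5% | 21% | 9% | 4% |
| 20% / 5% | 65% | 51% | 29% |
| 30% / 5% | 90% | 84% | 63% |

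Check of the first entry in the 20% / 0% row: one arm of 15 has 3 or more cases with probability 0.602, so at least one of the two dapagliflozin arms does with probability 1 − (1 − 0.602)² = 0.84.

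**Step 4: small early denominators.** With no placebo events, one DKA case exceeds 15% in any arm of 6 or fewer (1/6 = 16.7%; 1/7 = 14.3%). One pancreatitis case exceeds 5% in any arm of up to 19 (1/19 = 5.3%), so in every cohort 1 arm throughout.

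**The case against.** A reader might infer that the safety stop can never be computed when it is needed. The documents do not support that. Sections 19.1 and 19.6 both give an unblinding route, the codes are held independently, and adjusted rates can be calculated once that route is used. Monitoring is also more than quarterly: 19.5 has adverse events phoned in and reviewed the same day, 19.6 adds a review as each subject finishes, and 20.1 has patient-level withdrawal rules for DKA and pancreatitis.

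A reader might likewise infer that placebo adjustment is impossible for cohort 2. Its active-arm counts are visible because it is open label, and nothing excludes the cohort 1 placebo arm as comparator. That comparison would be non-concurrent and would set open-label patients against blinded ones; the plan neither names it nor discusses it.

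The pooled 10% is an illustration, not a prediction. Nothing says reviewers would hold a pooled rate against 15%, and six DKA cases might well raise a safety concern. Stretching the range to 13 of 80 would also be unfair, since that puts placebo patients in the denominator of a rate then adjusted for placebo.

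What remains is that none of these provisions puts counts by arm before the monitor at a routine review, sets an event count that prompts unblinding, or defines the quantity to be compared with 15% or 5%.

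**Conclusion.** The point holds as a conflict between stated rules, and it bears on patient safety. Section 19.9 relies on a between-arm quantity that the routine reviews in 19.1 and 19.6 cannot show. Access to it is discretionary, and the two sections differ on whether the monitor's recommendation is required. The undefined denominator moves the DKA trigger from 3 to 10 events with no placebo events, and from 4 to 15 with one. At an assumed true rate of 20% on dapagliflozin and none elsewhere, the chance of crossing runs from 84% down to 39%.

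The event counts are exact for the stated arm sizes. The probabilities rest on the assumed rates, on full cohort 1 enrolment and on a single look. Nothing here shows that the thresholds are wrong or that safety goes unmonitored.

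**What to change.** Leave the 15% and 5% thresholds as they are. At each 3-monthly review, have the already designated person not involved in patient care give DKA and pancreatitis counts by arm to the independent monitor only. Routine tables should not go to the investigators, who otherwise review jointly with the monitor and who receive unblinded data under the present wording of 19.1 and 19.6.

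The sponsor should define:
- the numerator, including whether the DKA definition cited in 20.1 applies to 19.9;
- the denominator: which arms, and whether enrolled, dosed or completed patients;
- the comparator and the method of adjustment;
- how cohort 2 is handled, acknowledging a non-concurrent, open-label versus blinded comparison if the cohort 1 placebo arm is used;
- the approach while arms are small.

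Sections 19.1, 19.6 and 19.9 must then be reconciled, including who may authorise unblinding. No particular stopping statistic is proposed here; that choice is the sponsor's.

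The cost is small: protocol wording, one short table per review and a brief closed portion of the meeting.

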## **20.0 Withdrawal of Subjects**

N/A: This study is not enrolling subjects. This section does not apply.

*20.1 Describe **anticipated** circumstances under which subjects may be withdrawn from the research without their consent.*

- a. Patient specific
  - i. Pregnancy
  - ii. Developing conditions included in the exclusion criteria
  - iii. Subjects decision to withdraw from the study
  - iv. Change in method of insulin delivery between insulin pumps to MDI or vice versa during the study. Also, patients who upgrade to the new "artificial pancreas" pump (Medtronic's MiniMed 670G hybrid) during the study will be withdrawn.
  - v. Side effects specific to study drugs
    1. 2 episodes of UTI.
    2. 2 episodes of mycotic genital infection.
    3. Significant persistent change in eGFR > 15 ml/min
    4. Significant nausea (defined as interfering with normal daily activities). *Those with mild or moderate nausea will continue for at least one more week. If they continue to experience significant nausea (defined as interfering with normal activities), they will discontinue the study.*

vi. DKA

Two episode of DKA (with no identifiable precipitating factors) as defined in the ADA (position statement on hyperglycemic crisis in diabetes (Diabetes Care, Volume 27, Supplement 1, January 2004)

vii. Pancreatitis

1. One episode of pancreatitis.

20.2 Describe any procedures for orderly termination.

*NOTE: Examples may include return of study drug, exit interview with clinician. Include whether additional follow up is recommended for safety reasons for physical or emotional health.*

Response: The principal investigator of the study can remove a participant from the research study without their approval if for any reason he/she feels is appropriate, including: severe side effect, injury or medical condition which may place you at risk of further complications if you continue to participate, failure to take the medication as instructed, failure to keep your scheduled appointments, cancellation of the study by the sponsor, or other administrative reasons.

If any of the subjects become pregnant during the period of study, they will need to withdraw from the study.

20.3 Describe procedures that will be followed when subjects withdraw from the research, including retention of already collected data, and partial withdrawal from procedures with continued data collection, as applicable.

Response: If a subject withdraws from the research, the data collected to that point will be used toward the research finding. If applicable the subject will have to bring back any unused research drug and or device. If necessary, they will be asked to complete an end of study visit for their safety.

